9.2.1 Adverse Events Definition and Reporting

Adverse Events (AE) will be assessed from the time a subject starts the study through the final follow up appointment. The SAFTEE (see description above in section 6.2) will be used to assess any AE's at each visit. This procedure involves asking subject open-ended questions (e.g. How have you been feeling since your last visit) as well as reviewing a specific list of side-effects associated with the study medication and having the subject respond yes/no.

Definitions

Adverse event means any untoward medical occurrence associated with the use of an intervention in humans, whether or not considered intervention-related (21 CFR 312.32 (a)).

An AE or suspected adverse reaction is considered "serious" (SAE) if, in the view of either the investigator or sponsor, it results in any of the following outcomes:

- death.
- a life-threatening adverse event,
- inpatient hospitalization or prolongation of existing hospitalization,
- a persistent or significant incapacity or substantial disruption of the ability to conduct normal life functions,
- a congenital anomaly/birth defect, or
- An important medical event that may not result in death, be life-threatening, or require hospitalization may be considered serious when, based upon appropriate medical judgment, they may jeopardize the participant and may require medical or surgical intervention to prevent one of the outcomes listed in this definition. Examples of such medical events include allergic bronchospasm requiring intensive treatment in an emergency room or at home, blood dyscrasias or convulsions that do not result in inpatient hospitalization, or the development of drug dependency or drug abuse.

Severity

Adverse events will be graded according to [name grading scale, e.g. CTCAE v5.0]. For AEs not included in the protocol defined grading system, the following guidelines will be used to describe severity.

- Mild Events require minimal or no treatment and do not interfere with the participant's daily activities.
- Moderate Events result in a low level of inconvenience or concern with the therapeutic measures. Moderate events may cause some interference with functioning.
- Severe Events interrupt a participant's usual daily activity and may require systemic drug therapy or other treatment. Severe events are usually potentially life-threatening or incapacitating. Of note, the term "severe" does not necessarily equate to "serious".

*An adverse event may be graded as severe but still not meet the criteria for a Serious Adverse Event (SAE). Similarly, an adverse event may be graded as moderate but still meet the criteria for an SAE. It is important for the PI to consider the grade of the event as well as its "seriousness" when determining whether reporting to the IRB is necessary.

Relationship to Investigational Product

All AEs must have their relationship to study intervention assessed by the clinician who examines and evaluates the participant based on temporal relationship and his/her clinical judgment. The degree of certainty about causality will be graded using the categories below. In a clinical trial, the study product must always be suspect.

- Definitely Related There is clear evidence to suggest a causal relationship, and
 other possible contributing factors can be ruled out. The clinical event, including an
 abnormal laboratory test result, occurs in a plausible time relationship to study
 intervention administration and cannot be explained by concurrent disease or other
 drugs or chemicals. The response to withdrawal of the study intervention
 (dechallenge) should be clinically plausible. The event must be pharmacologically or
 phenomenologically definitive, with use of a satisfactory rechallenge procedure if
 necessary.
- Probably Related There is evidence to suggest a causal relationship, and the
 influence of other factors is unlikely. The clinical event, including an abnormal
 laboratory test result, occurs within a reasonable time after administration of the
 study intervention, is unlikely to be attributed to concurrent disease or other drugs or
 chemicals, and follows a clinically reasonable response on withdrawal (dechallenge).
 Rechallenge information is not required to fulfill this definition.
- Potentially Related There is some evidence to suggest a causal relationship (e.g., the event occurred within a reasonable time after administration of the trial medication). However, other factors may have contributed to the event (e.g., the participant's clinical condition, other concomitant events). Although an AE may rate only as "possibly related" soon after discovery, it can be flagged as requiring more information and later be upgraded to "probably related" or "definitely related", as appropriate.
- Unlikely to be related A clinical event, including an abnormal laboratory test result, whose temporal relationship to study intervention administration makes a causal relationship improbable (e.g., the event did not occur within a reasonable time after administration of the study intervention) and in which other drugs or chemicals or underlying disease provides plausible explanations (e.g., the participant's clinical condition, other concomitant treatments).
- Not Related The AE is completely independent of study intervention administration, and/or evidence exists that the event is definitely related to another etiology. There must be an alternative, definitive etiology documented by the clinician.

Expectedness

The Principal Investigator will be responsible for determining whether an AE is expected or unexpected. An AE will be considered unexpected if the nature, severity, or frequency of the event is not consistent with the risk information previously described for the study intervention.

Reporting

For studies conducted under an IND, there are two types of Safety Reports submitted to FDA:

- 7-Calendar-Day FDA Telephone or Fax Report: The sponsor-investigator will directly notify the FDA, within 7 calendar days after initial receipt of the information, of any adverse event that is fatal or life-threatening, unexpected, and considered at least possibly related to the investigational product.
- 15-Calendar-Day FDA Written Report: The sponsor-investigator will directly notify the FDA within 15 calendar days after initial receipt of the information, of any serious adverse event (other than those that are fatal or life-threatening) that is unexpected and considered at least possibly related to the investigational product.

Serious Adverse Events which do not meet the criteria for expedited reporting will be reported to the FDA in the IND Annual Report.

Plan for reporting Unanticipated Problems Involving Risks to Subjects or Others (UPIRSOs), including Adverse Events, to the IRB.

The principal investigator will report the following types of events to the IRB:

Any incident, experience or outcome that meets ALL 3 of the following criteria:

- 1) Is unexpected (in terms of nature, specificity, severity, or frequency) given (a) the research procedures described in the protocol-related documents, such as the IRB-approved protocol and informed consent document and (b) the characteristics of the subject population being studied; AND
- 2) Is related or possibly related to participation in the research (*possibly related* means there is a reasonable possibility that the incident, experience, or outcome may have been caused by the procedures involved in the research); AND
- 3) Suggests that the research places subjects or others at greater risk of harm (including physical, psychological, economic, legal, or social harm) than was previously known or recognized.
 - UPIRSOs may be medical or non-medical in nature and include but are not limited to – serious, unexpected, and related adverse events and unanticipated adverse device effects. Please note that adverse events are reportable to the IRB as UPIRSOs only if they meet all 3 criteria listed above.

These UPIRSOs/SAEs will be reported to the IRB in accordance with IRB Policy 710, using the appropriate forms found on the website. All related events involving risk but not meeting the *prompt* reporting requirements described in IRB Policy 710 should be reported to the IRB in summary form at the time of continuing review. If appropriate, such summary may be a simple brief statement that events have occurred at the expected frequency and level of severity as previously documented. In lieu of a summary of external events, a current DSMB report can be submitted for research studies that are subject to oversight by a DSMB (or other monitoring entity that is monitoring the study on behalf of an industry sponsor).

7. Plan for reporting adverse events to co-investigators on the study, as appropriate the protocol's research monitor(s), e.g., industrial sponsor, DSMBs, study sponsors, funding and regulatory agencies, and regulatory and decision-making bodies.

For the current study, the following individuals, funding, and/or regulatory agencies will be notified (choose those that apply):

- x All Co-Investigators listed on the protocol.
- x NIH/NIAAA
- x Food and Drug Administration (Physician-Sponsored IND #137044)
- x Study Sponsor ([name]) and Novartis
- x Center for Translational Neuroscience on Alcoholism (CTNA) DSMB

The principal investigator, [name], will conduct a review of all adverse events upon completion of every study subject. She will evaluate the frequency and severity of the adverse events and determine if modifications to the protocol or consent form are required.

Adverse events that meet the criteria for a Serious Adverse Event will be reported to the IRB, NIAAA, the CTNA DSMB, study investigators, and to Novartis (the company providing mavoglurant) within 24 hours by phone or fax and in writing within 1 week.

9.2.2 Pharmacokinetics (if applicable)

Pharmacokinetic testing will be done to determine levels of mavoglurant in plasma. Blood will be drawn for this purpose at the first lab session (prior to initiation of mavoglurant) and twice at the 2nd lab session (after final dose of mavoglurant and again after alcohol drinking session. Language of this testing is included in the study informed consent form. A contract with Veeda Clinical Research Labs in Gujarat, India has been set up an specimen will be shipped appropriately upon study completion.

9.2.3 Biomarkers (if applicable)

N/A

9.3 Study Procedures

Recruitment, baseline assessments, physical exam, and psychological evaluation

Potential subjects will be recruited via posted advertisements in the local newspaper and brochures and other materials distributed in the community. We will also recruit via online methods such as FaceBook, CraigsList, online newspapers, Google Ads, etc. They will be initially screened for eligibility either by phone after giving verbal consent or via an online screener, the link for which will be provided in the study advertisements. After providing consent, participants will be asked to give their contact information so that they can be contacted regarding their eligibility. They will then proceed to complete the survey, which will be housed in a different account on Qualtrics, a secure website.

Based on eligibility, participants will be scheduled for an intake appointment and complete consent via REDcap (or mail or in-person if necessary). All questionnaires, medical history, and psychological evaluation will be conducted remotely via video chat (e.g. Zoom, FaceTime, etc). If the study participant does not have internet access or a device capable of this form of communication, we will conduct the appointment over the phone or in person. Each participant will be asked comprehension questions to ensure they understand the study and will be asked to sign the consent form. Prior to all in person study appointments, COVID-19 screening questions will be asked. All participants will receive a signed copy of the consent form to retain for their records. The research assistant will schedule a physical exam, including an EKG, routine laboratory work, and hepatic, kidney and thyroid function tests. A detailed medical history will be obtained from all subjects and pregnancy tests for all females. Subject characteristics and medical history will be reviewed by the PI to ensure that the subject meets all the eligibility criteria. The study physician ([name]) will review their eligibility based on their medical history and EKG.

The psychological evaluation will be completed and reviewed by a licensed psychologist after all inventories/assessments are collected. If a subject is deemed at risk, or questionable, at the time of the evaluation, the clinical psychologist will be contacted immediately and asked to reach out to the participant as soon as possible.

Lab Session 1

See appendix for detailed procedure sheet. Participants will arrive at the Hospital Research Unit (HRU), Church Street Research Unit (CSRU), or Masonicare at 8:15am. We will collect BAC, urine toxicology, and conduct paper and pencil baseline questionnaires. At 9:00am,

participants will be provided breakfast. They will then complete additional study assessments. We will put an IV catheter in the participant's arm at 11:00am and we will draw the initial set of labs. At 12:00pm, participants will be given their first drink of 80-proof vodka with a non-carbonated mixer of their choice and will be instructed to drink it in 15 minutes. They will continue to receive successive doses of alcohol in 6 equal portions (every 15 minutes) over a 90-min period designed to raise their blood alcohol levels to 80 mg/dl: we chose this dose because this the legal limit of intoxication and is close to the peak BAC we have observed in prior ADP sessions (with approx. 200 heavy drinkers) and is similar to the alcohol dose used in a previously completed similar protocol with another drug (HIC #0602001068). Alcohol dosing will be calculated using published gender specific algorithms based on estimated body water determined from height, weight (obtained at physical exam), and age and translated into ml of 80-proof vodka (Curtain & Fairchild, 2003). Regardless of the amount of vodka required, the amount of mixer will be adjusted so that the total volume of fluid will be constant. These methods of alcohol administration have been safely used by our group (Jatlow, et al., 2014), with volunteers who had similar drinking profiles. At 12:15pm, a blood pressure cuff will be placed on his/her arm to monitor vitals throughout the lab session. Safety labs will be drawn and blood samples will be collected at regular intervals (at baseline and every 15 minutes during the lab session and then hourly for the next 3 hours) to assess blood alcohol levels and to assess Mavoglurant levels. They will complete paper and pencil questionnaires about mood, medication and alcohol effects at regular time intervals, as well as the Body Sway Task.

At 2pm, subjects will be given lunch and will be monitored for any remaining alcohol effects. BAC levels will be taken every 30 minutes until the level falls to less than .02 (about 4 hours). Participants will be allowed to leave when their BAC falls to below .02 or at 6pm, whichever comes first. All participants will be provided with transportation to and from lab session.

Outpatient Treatment

At the commencement of drinking session 1, participants will be sent home with the study medication for the full period. If their second lab session is not scheduled within the designated timeframe, the participant will come in for their first medication appointment and be sent home with their medication that day. They will take their medication daily (in person or on video chat – 10min) at approximately 10am. They will be observed taking the study medication, for 7-10 days (to achieve steady state levels). This will ensure compliance with medication and allow us to monitor side effects daily. The last dose of study medication will be at 8:15 on the morning of their Lab Session 2. Participants will be asked to abstain from alcohol during the outpatient medication period; our rationale for requiring this is because this is a study to examine alcohol-drug interactions and we want to study these interactions in a controlled laboratory session.

Lab Session 2

See appendix for detailed procedure sheet. Participants will arrive at the Hospital Research Unit (HRU), Church Street Research Unit (CSRU), or Masonicare at 8:15am. They will be instructed to take their last dose of study medication. We will collect BAC, urine toxicology, and provide them with breakfast. Following breakfast, they will complete study assessments/questionnaires. We will put an IV catheter in the participant's arm at 11:00am and we will draw the initial set of labs. At 12:00pm, participants will be given their first drink of 80-proof vodka with a non-carbonated mixer of their choice and will be instructed to drink it in 15 minutes. They will continue to receive successive doses of alcohol in 6 equal portions (every 15 minutes) over a 90-min period designed to raise their blood alcohol levels to 80 mg/dl. Safety labs will be drawn and blood samples will be collected at regular intervals (at baseline and every 15 minutes during the lab session and then hourly for the next 3 hours) to assess blood alcohol levels and to assess Mavoglurant levels. They will complete paper

and pencil questionnaires about mood, medication and alcohol effects at regular time intervals, as well as the Body Sway Task.

At the end of the drinking session, the participant will be given lunch. They will be monitored for any remaining medication and alcohol effects. BAC levels will be taken every 30 minutes until the level falls to less than 0.02 (about 4 hours). Participants will be allowed to leave at approximately 6pm or when their BAC falls to below 0.02. All participants will be provided with transportation to and from lab session. The following morning participants will go to Quest for a blood draw and urine collection.

Follow Up Interviews

Subjects will receive phone calls on the two days following lab session 2 to see how they are doing and to assess any remaining side effects from the medication. Subjects will also participate in a 30-minute follow-up interview at one week after lab session 2. During this appointment, we will assess participants for any lingering side effects of the medication and obtain information about their drinking over the follow up period.

Payments for Participation (Economic Considerations)

Subjects will have the opportunity to receive up to \$630 for completing all parts of the study. Payment for the intake interview will be \$50. They will receive an additional \$65 for the physical examination/ in-person intake and up to \$20 for completing the MSDM task. Subjects will also receive \$140 for participating in the 1st laboratory session and \$200 for completing the 2nd laboratory session. Additionally, subjects will receive \$10 to take their study medication dose (7-10 days), for up to a total of \$100 and \$25 for the blood draw the morning after the second drinking session. Subjects will be paid \$30 for completing the one week follow-up appointment. If a subject is asked to come back in for a repeat lab appointment (blood work or EKG), he/she will be paid \$25. Subjects will be reimbursed for parking.

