7.1 Primary Objective

The primary objective of this study is to evaluate the safety and tolerability of mavoglurant when used in combination with a moderate dose of alcohol in healthy social drinkers.

Specific Aim 1: To evaluate the effect of mavoglurant on blood chemistries, urine toxicology and physiological safety measures before and after alcohol administration.

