9.3.6 End of Study and Follow-up

After the second lab session staff will check in with the subject via phone. A final, follow-up visit will be conducted. Adverse events will be monitored 1 week after the second lab session. The participant will come in-person for blood, along with psychophysiological safety measures (heart rate, blood pressure, etc.) only when blood pressure is signfically elevated at lab session. If a subject request a copy of results (e.g. blood analytes), I de-identified copy will be provided upon approval of the PI.

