10.18 Publication Plan

Any resulting publications will be done with approval of the PI, Sponsor, and Novartis.

11 Appendices

р	

APPROVED BY THE YALE UNIVERSITY IRB 11/22/2023

APPROVED BY THE YALE UNIVERSITY IRB 11/22/2023

TIME	START OF DRINKING SESSION PROCEDURES
Prior to	Confirm [name] signed off on EPIC orders
arrival	Confirm participant breakfast and lunch were ordered from HRU and transport was setup.
RA	Confirm covid questions were filled and negative rapid covid test and send both to [contact] and [contact] .
	Pick up study alcohol and meds from IDS
	Bring to lab: alcohol, participant binder, participant folder, CTNA laptop, fruit juice mixer and frozen breakfast option (if needed).
	Confirm participant was added to OnCore
8:15 am	*RA and participant to have a mask on in lab (confirm extra masks are at lab)
RA	Give participant meds (if first dose is scheduled for tomorrow)
	Meet participant in 1st floor lobby and walk them to the CSRU on the 4th floor
	Get study cart from OnCore/Epic Suite #404, code 9224#, Key holder (PIN 3636)
	Urine drug screen and pregnancy test (*RA to send urine to Quest): Neg Pos
	Record time of last drink Amount of last drink
	Instruct participant on using both (BAC and CO) step out of room.
	BAC Level: CO Level:
	*If BAC is positive, notify [name] [contact]
	Concurrent medications, TLFB, SAFTEE
	Collect subject's cigarettes (if applicable) Smoker: Nonsmoker:
	Height: inches (Shoes off) Weight: kgs lbs.
	*For data only. IDS will be using height and weight from PE for alcohol calculations.
	Fill out Quest form for today

	Baseline PACKET #1: YCS Long, AES, BAES, BIS, BIS/BAS, UPPS, SRHI, PROMIS Sleep
	and Impairment Measures, AUDIT-C, W9
	Baseline Assessments
	Body Sway Task (Confirm data is recording and showing weight, if not restart task)
	CPT
	SRT
	CRT
9:00 am	Give subject breakfast. Time: (Ensure they eat, so they don't have an empty stomach)
RA	*NO FOOD AFTER 10AM, UNTIL AFTER DRINKING SESSION IS OVER
11:00 am	Place heplock in non-dominant arm (DO NOT USE A RUNNING IV)
NURSE	*If you experience any problems or have any concerns with the IV placement, please contact study staff PRIOR to placing IV.
	Record actual time of blood draw:
	DRAW "-60min" BAL (blue microtube)
	Health Profile (CMP, CBC w/diff, TSH, Phosporous, Magnesium, Uric Acid)
	2 Marble/gold 5ml top tubes (spun) and 1 lavender tube 4ml (unspun) *RA to send samples Quest

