	1 MAV lavender 10ml pre "-60" plasma level. Put two lables on tube. Process in cold centrifuge (-80 degrees freezer or dry ice)
	Urine (Urinalysis) *RA to send samples to Quest
11:00 am RA	Place labled Health Profile (2 Marble/gold 5ml top tubes (spun), 1 lavender tube 4ml
101	(unspun), and urine sample in Quest box on 4th floor outside of room 401.
	Call Quest for pickup or online (ensure they arrive prior to building closing)
	Record dose of alcohol from Pharmacist and mixer
	Alcohol Dose (vodka): ml Mixer (Juice): ml
	Bathroom break and ensure participant has water to drink.
	Premix all 6 drinks Juice (of their choice) and vodka (0.03 mg%) and cap securely.
	Keep drinks on ice.
	Setup Zoom on laptop to communicate during drinking session.

11:55 pm	Bring all 6 drinks into room with participant. Bring packets 2-7 into room.
RA	Set up for drinking session and READ study spiel to subject.
12:00 pm	Drink #1, Juice (of their choice) and vodka (0.03 mg %)
RA	Instruct participant that s/he has 15 minutes to drink cup #1 and to pace their drinking so it is consumed over the entire 15-minute period. (start timer count up)
12:15 pm NURSE	BP: Pulse: (BP cuff on arm opposite IV, stays on until the end of
None	the drinking session)
	DRAW "+15min" BAL Record actual time of blood draw:
12:15 pm	PACKET#2: YCS, AES
RA	Drink #2, Juice (of their choice) and vodka (0.03 mg %)
	Instruct participant that s/he has 15 minutes to drink it (start timer)
	BP: Pulse:
12:30 pm	DRAW "+30min" BAL Record actual time of blood draw:
NURSE	
12:30 pm	PACKET #3: YCS, AES
RA	Drink #3, Juice (of their choice) and vodka (0.03 mg %)
	Instruct participant that s/he has 15 minutes to drink it (start timer)
12:45 pm	BP: Pulse:
NURSE	DRAW "+45min" BAL Record actual time of blood draw:
12:45 pm	PACKET #4: YCS, AES, BAES
RA	Drink #4, Juice (of their choice) and vodka (0.03 mg %)
	Instruct participant that s/he has 15 minutes to drink it (start timer)
1:00 pm	BP: Pulse:
NURSE	DRAW "+60min" BAL Record actual time of blood draw:
1:00 pm	PACKET #5: YCS, AES
RA	Drink #5, Juice (of their choice) and vodka (0.03 mg %)
	Instruct participant that s/he has 15 minutes to drink it (start timer)
1:15 pm	BP: Pulse:
NURSE	DRAW "+75min" BAL Record actual time of blood draw:
1:15pm	PACKET #6: YCS, AES
RA	Drink #6, Juice (of their choice) and vodka (0.03 mg %)

	Instruct participant that s/he has 15 minutes to drink it (start timer)
1:30 pm	Have subject rinse mouth out with water

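### Lab Session 1 schedules no blood pressure or heart rate reading before the first drink, so the no-drug session yields no within-session change from a pre-alcohol value for these measures

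*Combined protocol and SAP*

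**What the plan says.** Aim 1 (section 7.1) is to evaluate the effect of mavoglurant on "blood chemistries, urine toxicology and physiological safety measures before and after alcohol administration". Section 9.3.6 shows what the last of these means by referring to "psychophysiological safety measures (heart rate, blood pressure, etc", and section 8.2 puts heart rate and blood pressure among the primary outcomes.

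For Lab Session 1, section 9.3 states "At 12:00pm, participants will be given their first drink of 80-proof vodka" and, later in the same paragraph, "At 12:15pm, a blood pressure cuff will be placed on his/her arm to monitor vitals throughout the lab session". The procedure sheet in section 11 has its first vital-signs field in the 12:15 row: "BP: Pulse: (BP cuff on arm opposite IV, stays on until the end of". That sheet reads as the Session 1 sheet, because its 8:15 row contains "Give participant meds (if first dose is scheduled for tomorrow".

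The same sheet does plan a pre-drink baseline for other measures. Its first questionnaire packet begins "Baseline PACKET #1: YCS Long, AES, BAES, BIS, BIS/BAS", followed by body sway and the three computer tasks. At 11:00 a nurse is with the participant ("Place heplock in non-dominant arm (DO NOT USE A RUNNING IV") and takes the -60 min samples, but that row has no BP/pulse field.

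Sections 9.3.1 and 9.3.5 list vitals or psychophysiological measures for both lab sessions without a time. For Session 2, section 9.3 mentions no reading before the first drink and refers to an appendix sheet that is not in the text available.

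**The concern.** The aim names a before and an after, but the only timed sources for Session 1 supply just the after. For BP and heart rate, the response to alcohol in the no-drug session can be described only as a level reached once drinking has begun. Section 8.2.2 also plans to compare BP and heart rate responses between the mavoglurant session and the no-drug session. Without a Session 1 baseline, that comparison is limited to levels at matched times after the drink. If Session 2 does have a pre-drink reading, the two sessions are not measured alike.

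Section 9.5.1 does not resolve this. It covers BP and heart rate only through a general sentence on mixed models for quantitative outcomes and does not say which reading is the baseline.

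**Working it through.** The plan states no figure to reproduce. The check sets the timed entries against the first drink.

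**BP/pulse fields on the sheet, in minutes from the 12:00 drink:** 15, 30, 45, 60, 75, 120, 180, 240, 270, 300, 330, 360. That is 12 fields, of which 0 fall at or before minute 0. The 8:15, 9:00, 11:00, 11:55 and 12:00 rows have none.

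**Measures recorded after the first drink:** BP/pulse, blood alcohol, breath alcohol, YCS, AES, BAES, body sway, CPT, SRT, CRT = 10. A pre-drink entry exists for breath alcohol (8:15), blood alcohol (11:00), the three scales (baseline packet) and the four tasks (baseline assessments) = 9. BP/pulse is the exception. The narrative and the sheet give the same 12:15 start, so a line lost from one of them is an unlikely explanation.

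**Can the 12:15 reading stand in?** Only in part. It follows 15 minutes of drinking and one of six equal portions, 1/6 = 16.7% of the alcohol, assuming drink 1 is finished as instructed. This counts alcohol swallowed. It does not estimate bias.

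**What each contrast needs.** Let *r* be the resting effect of the drug on BP or heart rate, and *g* the additional effect of the drug when alcohol is present. Under randomisation, the expected differences between arms are:

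| Reading | Session 1 (before any drug) | Session 2 |
|---|---|---|
| Before the drink | 0 | *r* |
| After the drink | 0 | *r* + *g* |

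- The combined effect *r* + *g* needs only the Session 2 post-drink readings, which do not depend on the Session 1 gap.
- The interaction within Session 2, (*r* + *g*) − *r* = *g*, needs a Session 2 pre-drink reading. Whether one is scheduled is not known from the text.
- The alcohol response without drug in Session 1, and any between-session comparison of change, needs a Session 1 pre-drink reading. This is the confirmed gap.

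**Reach of a change made now.** Section 7.2 mentions the first 10 completers and a further 14: 10 + 14 = 24. Against the planned 28, that leaves 28 − 24 = 4, or 4/28 = 14%. If the pre-drink value were a required covariate and no earlier record held one, 24/28 = 86% of completers would be dropped, contrary to the all-available-data principle in section 9.5.10.

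**The case against.** The strongest reply is that nothing essential is lost. Aim 1 does not say same day. Section 8.2 places BP and heart rate in the outpatient period and during alcohol administration, and section 9.3.5 ticks them at the physical exam and the medication visits. The before-and-after comparison in section 9.5.1 names laboratory measures, not BP or heart rate. Nobody has taken the drug in Session 1, so the drug effect comes from comparing arms in Session 2.

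Much of this stands. A reader might infer that the trial has no alcohol-free BP or heart rate at all. It does, on other days. Those readings are weaker as a reference: they come from other days and settings, and medication visits may be by video. A reader might also infer that the randomised safety comparison fails, or that drug-alone and interaction effects can never be separated. The documents support neither. The arm comparison on alcohol is intact, and alcohol-free outpatient readings bear on the resting drug effect.

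Nor do the documents support claiming the same gap in Session 2. The sheet to which section 9.3 refers may have been lost in text extraction.

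Finally, the untimed vitals entry for Day 0 does not exclude a pre-drink reading in practice. It does not schedule one either, and both timed sources start at 12:15. What remains is a mismatch between the aim and the Session 1 schedule.

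**Conclusion.** The point holds for Session 1. No pre-drink BP or heart rate reading is scheduled (0 of 12 fields), so a within-session change from a pre-alcohol value is not available for these primary safety measures in the no-drug session. For Session 2 the timing needs confirming, and no defect is asserted.

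The consequence is moderate. The main combination-safety contrast survives. The no-drug alcohol response and the between-session comparison of change are lost for BP and heart rate, unless records hold unscheduled values. The conclusion assumes that the sheet shown is the Session 1 sheet and that no order outside the document adds a reading. The count of about 24 completers assumes that the two groups in section 7.2 do not overlap and make up all completers to date.

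**What to change.** - **Schedule.** Add a BP/pulse reading at the 11:00 nurse contact in Session 1, alongside the -60 min draw. Confirm that Session 2 has the same reading at the same point in the sequence, or add it. State the time in section 9.3 and on both sheets.
- **Analysis (section 9.5.1).** Keep the comparison of arms on BP and heart rate on alcohol, using all available data, as the main contrast. Enter the pre-drink reading as a repeated time point in the mixed model, not as a required covariate, so that participants without it stay in.
- **Participants already completed.** Check source records and report how many have a pre-drink value, by session and arm. Where it is missing, use alcohol-free outpatient or physical exam readings as a supportive reference. State that, for those participants and sessions, a resting drug effect cannot be separated within the session from a drug-alcohol interaction.

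The cost is a few minutes of nurse time per session at an existing contact, edits to two sections and the sheets, and one record check. The drawback is limited gain: if earlier records hold nothing, only about 4 participants would have the reading, and any estimate of change from it would be descriptive.
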